12.3.2 Secondary Efficacy Analyses

The secondary efficacy variables for all subjects (i.e., recommended dose or any other dose level in Parts A and B of Induction Therapy) are as follows:

- The percentages of subjects with at least a 1-point improvement in their mMES from Baseline (Week 0) to Week 12.
- The percentages of subjects with at least a 1-point improvement in their modified Baron endoscopic score from Baseline (Week 0) to Week 12.
- The mean change in UCEIS (0 to 8) and subscores from Baseline (Week 0) to Week 12.
- The percentage of subjects with a mucosal healing (the mMES \leq 1) at Week 12.
- The change from Baseline (Week 0) in total Mayo Clinic score (0 to 12) at Week 12.
- The change from Baseline (Week 0) in partial Mayo Clinic scores (0 to 9; without sigmoidoscopy) at Weeks 2, 4, 6, 8, 10, and 12.

- The percentages of clinical response (the change from Baseline in the total Mayo Clinic score ≤ -3 and the percentage change from Baseline in the total Mayo Clinic score $\leq -30\%$ to Week 12, with an accompanying decrease in the rectal bleeding subscore of at least 1 point or an absolute rectal bleeding subscore of ≤ 1).
- The percentages of clinical remission (a total Mayo Clinic score ≤ 2 and no subscores > 1) at Week 12.

Treatment (each KHK4083 dose level versus placebo) comparisons by cohort will be performed with the linear model for all secondary efficacy analyses of continuous variables.

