7.2 Analysis of secondary efficacy endpoints

The secondary efficacy variables for all subjects (i.e., recommended dose or any other dose level in Parts A and B of Induction Therapy) are listed in the following table.

Efficacy Variables	Definition
Improvement in the Mucosa (Measured by modified Mayo endoscopy subscore [mMES]) (Week 12)	Percentage of subjects with at least a 1-point improvement in their mMES (0 to 3) from Baseline (Week 0) to Week 12.
Improvement in the Mucosa (Measured by modified Baron scoring system) (Week 12)	Percentage of subjects with at least a 1-point improvement in their modified Baron endoscopic score (5-point scale) from Baseline (Week 0) to Week 12.
Improvement in the Mucosa (Measured by Ulcerative Colitis Endoscopic Index of Severity [UCEIS]) (Week 12)	A mean change in the UCEIS (scores from 0 to 8, based on findings of vascular pattern, bleeding, and erosions/ulcers) from Baseline (Week 0) to Week 12.
Mucosal Healing (Week 12)	The percentage of subjects with mMES of 0 or 1 at Week 12.
Clinical Improvement (Week 12)	Mean change from Baseline (Week 0) at Week 12, in the total Mayo Clinic score (0 to 12).
Clinical Improvement (Weeks 2, 4, 6, 8, 10, and 12)	Mean changes from Baseline (Week 0) in the partial (excludes endoscopy subscores) Mayo Clinic score (0 to 10).
Clinical Response (Week 12)	A reduction in the total Mayo Clinic score of at least 3 points and a decrease of at least 30% from Baseline (Week 0) to Week 12, and a reduction in the rectal bleeding subscale of at least 1 point from Baseline (Week 0) to Week 12 or an absolute rectal bleeding score of 0 or 1 at Week 12.
Clinical Remission (Week 12)	A total Mayo Clinic score of ≤ 2 and no subscores > 1 .

All secondary efficacy variables will be summarized by treatments (each KHK4083 dose level and placebo). Change from Baseline in UCEIS, total Mayo Clinic score as well as Baseline and Week 12 will be summarized by treatments. Partial Mayo Clinic scores and changes from Baseline will be summarized from Baseline to Week 12 by treatments. Summaries statistics and 95% CI will be presented and estimated as described in section 7.1 of this SAP.

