A comparison between treatments (each KHK4083 dose level versus placebo) will be performed using an ANCOVA model with changes from Baseline in UCEIS, total Mayo Clinic score and partial Mayo Clinic score at Week 12 as dependent variables, treatment as fixed effect and baseline value as covariate. The number of subjects and the number of subjects considered in the model will be provided by treatment. The adjusted means for treatments (least squares means) and the relative 95% CIs will be presented. The difference between the adjusted means for each treatment groups from placebo (Difference in Least Squares Mean from Placebo) will be calculated with the relative 95% CI and p-value. Least squares means with 95% CIs and differences in least squares mean from placebo with 95% CIs will be graphically presented.

	Forms			
	Title	Statistical Analysis Plan Template		
	Code	Version	Effective Date	Page
	FRM_ST03_032	01	23 Apr 2015	31 of 53

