To take into consideration about the repeat measurements in partial Mayo Clinic score, an analysis using a Mixed Model for Repeated Measures (MMRM) will be performed. A comparison between treatments (each KHK4083 dose level versus placebo) will be performed using a MMRM with the change from baseline in partial Mayo Clinic scores during Double-Blind Therapy Period and Double-Blind Therapy Follow-up Period as dependent variable, treatment as fixed effect and baseline value as covariate, and visit as random effects. The interaction between treatment and visit also will be included. An unstructured covariance matrix will be considered and the Kenward-Roger adjustment will be used for the degrees of freedom. In the case that the unstructured covariance matrix cannot be used, a compound symmetry will be used as the covariance matrix instead of the unstructured one. The number of subjects, the number of subjects considered in the model and the number of observations considered in the model will be provided by treatments. The adjusted means for treatments (least squares means) at each visit and the relative 95% CIs will be presented. The differences between the adjusted means for treatments from placebo (Difference in Least Squares Mean from Placebo) at each visit will be calculated with the relative 95% CIs and p-values. If MMRM cannot be applied due to the issue that the parameters cannot be estimated appropriately, the structure of covariance matrix will be changed to compound symmetry. If MMRM cannot be applied by using the covariance matrix of compound symmetry, this analysis using MMRM will not be applied.

SAS® code

```
proc mixed data=dat001 ORDER=DATA;
  class visit tmt;
  model chg=tmt visit baseline tmt*visit /solution ddfm=kr;
  repeated visit / type=un subject= subjectj;
  lsmeans tmt*visit / slice=tmt pdiff diff alpha=0.05 cl;
  lsmeans tmt / pdiff diff alpha=0.05 cl;
run;
```

For the following scores, to show changes in score during the study, those scores will be summarized by treatments.

- Subscores of Mayo Clinic Score other than mMES: “Stool Frequency”, “Rectal Bleeding”, and “Physician’s Global Assessment”
- Modified Baron Endoscopic Score
- Subscores of UCEIS: “Vascular pattern”, “Bleeding”, and “Erosions and ulcers”

	Forms			
	Title	Statistical Analysis Plan Template		
	Code	Version	Effective Date	Page
	FRM_ST03_032	01	23 Apr 2015	34 of 53

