9.4.1 Tables for Un-Blinded 12 Week Induction Therapy Data

Number	Title
Table 14.1.1	Disposition of Subjects for Induction Therapy Period
Table 14.1.4.1	Demographics (Safety Analysis Set)
Table 14.2.1.1	Baseline and Change from Baseline of Modified Mayo Endoscopic Score (MMES) at Week 12 (induction Therapy)
Table 14.2.1.2	Analysis of Change from Baseline in MMES at Week 12
Table 14.2.2.1	Baseline and Change from Baseline in UCEIS at Week 12
Table 14.2.2.2	Baseline and Change from Baseline in Total Mayo Clinic Score at Week 12
Table 14.2.2.3	Partial Mayo Clinic Score during Induction Therapy
Table 14.2.2.4	Clinical Improvement (%) at Week 12 in MMES, Modified Baron Endoscopic Score, Mucosal Healing, Clinical Response and Clinical Remission
Table 14.2.2.5.1	Analysis of Change from Baseline in UCEIS at Week 12
Table 14.2.2.5.2	Analysis of Change from Baseline in Total Mayo Clinic Score at Week 12
Table 14.2.2.5.3	Analysis of Change from Baseline in Partial Mayo Clinic Score at Week 12

Forms

Title Statistical Analysis Plan Template

Code

Version

Effective Date

Page

FRM_ST03_032

01

23 Apr 2015

48 of 53

Number	Title
Table 14.2.3.9.1	Baseline and Change from Baseline in Mayo Clinic Score - Stool Frequency during 12 Week Induction Therapy
Table 14.2.3.9.3	Baseline and Change from Baseline in Mayo Clinic Score - Rectal Bleeding during 12 Week Induction Therapy
Table 14.2.3.9.7	Baseline and Change from Baseline in Modified Baron Endoscopic Score at 12 Week Induction Therapy
Table 14.2.3.9.9	Baseline and Change from Baseline in UCEIS Subscore - Vascular Pattern at 12 Week Induction Therapy
Table 14.2.3.9.11	Baseline and Change from Baseline in UCEIS Subscore - Bleeding at 12 Week Induction Therapy
Table 14.2.3.9.13	Baseline and Change from Baseline in UCEIS Subscore - Erosions and Ulcers at 12 Week Induction Therapy
Table 14.3.1.1.3	Overall Summary of Treatment Emergent Adverse Events during Induction Therapy
Table 14.3.1-2.2	Treatment-Emergent Adverse Events by System Organ Class and Preferred Term during Double-Blind Induction Therapy Period
Table 14.3.1.2.5	Treatment-Related Treatment-Emergent Adverse Events by System Organ Class, Preferred Term during Double Blind Induction Therapy.
Table 14.3.1.4.2	Serious Treatment-Emergent Adverse Events by System Organ Class and Preferred Term during Double-Blind Induction Therapy Period

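### SAP 7.2 compares only three Week 12 totals with placebo, so the UCEIS subscores have no placebo comparison anywhere, and partial Mayo at Weeks 2-10 has none in the 12-week outputs

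*SAP*

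**What the plan says.** Protocol 12.3.2 lists the secondary variables. The continuous ones are:

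- UCEIS with its components: "The mean change in UCEIS (0 to 8) and subscores from Baseline (Week 0) to Week 12".
- Total Mayo: "The change from Baseline (Week 0) in total Mayo Clinic score (0 to 12) at Week 12".
- Partial Mayo: "partial Mayo Clinic scores (0 to 9; without sigmoidoscopy) at Weeks 2, 4, 6, 8, 10, and 12".

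It closes with a general rule, each dose level against placebo: "comparisons by cohort will be performed with the linear model for all secondary efficacy analyses of continuous variables".

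SAP 3.4.2 keeps the UCEIS subscores and all six partial Mayo visits as secondary endpoints. The analysis text in SAP 7.2 is narrower. The ANCOVA takes "changes from Baseline in UCEIS, total Mayo Clinic score and partial Mayo Clinic score at Week 12 as dependent variables". For the earlier visits it says only: "Partial Mayo Clinic scores and changes from Baseline will be summarized from Baseline to Week 12 by treatments". The subscores are missing from the 7.2 variable table and return in SAP 7.3 as scores to be summarised by treatment.

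SAP 7.3 also plans an MMRM on change in partial Mayo over the Double-Blind Therapy Period and its follow-up, with differences from placebo at each visit. SAP 4.1 defines that period to include induction. If an unstructured covariance cannot be used, the SAP falls back to compound symmetry, and after that: "If MMRM cannot be applied by using the covariance matrix of compound symmetry, this analysis using MMRM will not be applied".

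SAP 4.5 says that the tables for the unblinded 12-week data are those in 9.4.1, and that their results inform the proof-of-concept determination.

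**The concern.** The protocol sets a rule with no exceptions. The SAP carries it out for part of the list and does not say that it has stopped short. SAP 4.5 is the section for changes to the planned analysis, but it deals only with unblinding and the data cut. Protocol 12.8 asks for deviations from the protocol's analysis to be explained in the study report, and one that nobody has noticed is easily left out.

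The secondary objective for partial Mayo runs from Week 2 through Week 12. At the 12-week cut, five of its six visits would be reported arm by arm with no estimate against placebo, so onset of effect is not estimated. The subscores would show, within each arm, which endoscopic component moved, but never relative to placebo.

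**Working it through.** **The plan's own figures.** Protocol 12.3.4 and SAP 3.2 give 51 evaluable subjects and 15% dropout: 51 / (1 - 0.15) = 60 randomised, as stated. The arms also agree: 9 + 18 = 27 on the recommended dose and 9 + 6 = 15 on placebo. The count below does not depend on these figures. The 51 is used only to judge the MMRM.

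**Comparisons implied by Protocol 12.3.2.** Three dose levels are each compared with placebo.

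| Continuous secondary variable | Variable-visits | x 3 doses | In SAP 7.2 ANCOVA |
|---|---|---|---|
| UCEIS total, Week 12 | 1 | 3 | 3 |
| UCEIS subscores (vascular pattern, bleeding, erosions/ulcers), Week 12 | 3 | 9 | 0 |
| Total Mayo, Week 12 | 1 | 3 | 3 |
| Partial Mayo, Week 12 | 1 | 3 | 3 |
| Partial Mayo, Weeks 2, 4, 6, 8, 10 | 5 | 15 | 0 |
| Total | 11 | 33 | 9 |

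Shortfall in SAP 7.2: 33 - 9 = 24, which is 15 for partial Mayo and 9 for the subscores.

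**What the rest of the SAP supplies.** The MMRM in SAP 7.3 (Table 14.2-3.8.4) gives the 15 partial Mayo differences in the final outputs, if it is fitted. That leaves 24 - 15 = 9 subscore differences with no model anywhere.

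**What the 12-week outputs supply.** In SAP 9.4.1 the secondary tables titled as analyses are 14.2.2.5.1 to 14.2.2.5.3, all at Week 12. The MMRM is not listed. Table 14.2.2.3, "Partial Mayo Clinic Score during Induction Therapy", corresponds to the summaries in SAP 7.2, which carry arm-wise 95% CIs. The subscores appear as baseline and change tables (14.2.3.9.9, 14.2.3.9.11 and 14.2.3.9.13). At this cut all 24 differences are absent.

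**Size of the MMRM.** Distinct scheduled weeks in its double-blind and follow-up scope: Weeks 2-12, 6 visits; Weeks 16-52, 10; Week 26, 1; Weeks 56-64, 3. Total 6 + 10 + 1 + 3 = 20. An unstructured matrix then has 20 x 21 / 2 = 210 parameters for about 51 subjects, with the later weeks seen only in subsets. A model restricted to the six induction visits has 6 x 7 / 2 = 21.

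**The case against.** The strongest reply is that most of the gap is already filled. An MMRM with baseline as covariate is a linear model suited to repeated measures. It yields placebo differences with 95% CIs at Weeks 2-10, and the SAP drops it only if both covariance structures fail. This stands for the final analysis. A reader might infer that partial Mayo at Weeks 2-10 is never compared with placebo, or that all 24 differences are lost for good; SAP 7.3 shows otherwise. Outright dropping may well be unlikely. Fallback to compound symmetry is easier to foresee, and it would impose one correlation on visits from Week 2 to Week 64.

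Second, the 12-week outputs are not empty on these endpoints. Subscore changes are tabulated by treatment, and partial Mayo has arm-wise 95% CIs. That also stands. What is missing is the difference from placebo.

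Third, a reader might infer that the proof-of-concept decision turns on these comparisons. The documents do not support that. The criteria are not stated, and SAP 4.5 ties the cut to the primary and main secondary endpoints. The main secondary endpoint is mMES change at the other doses. Nor does Protocol 12.3.2 say that every comparison must be ready at the 12-week cut.

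Fourth, the protocol is not uniform on the subscores. Its objectives and Appendix 1 define UCEIS improvement by the total alone, while Protocol 10.2 and 12.3.2 and SAP 3.4.2 include the subscores. The 9 subscore differences rest on those latter sections, one of which is the protocol's own section on secondary efficacy analyses.

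The exploratory status of all analyses (Protocol 12.3.5) limits the consequence. It also means that adding estimates uses no error allowance.

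**Conclusion.** The SAP narrows a protocol-specified analysis without recording it. Across the whole SAP, 9 differences from placebo, those for the three UCEIS subscores, have no model. A further 15, for partial Mayo at Weeks 2-10, depend on one exploratory model that is large for the sample, may be dropped, and is not among the 12-week outputs. The primary mMES comparison and the three Week 12 totals keep their comparison with placebo, so this is a worthwhile, inexpensive repair and does not threaten the main result.

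This rests on two assumptions. The first is that the subscores are secondary variables, as Protocol 12.3.2 and SAP 3.4.2 list them. The second is that the 9.4.1 tables contain what their titles and the text of SAP 7.2 and 7.3 indicate, since the table shells are in a separate document.

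**What to change.** 1. In SAP 7.2, add the existing ANCOVA (treatment, baseline value) for the three UCEIS subscores at Week 12.
2. For partial Mayo at Weeks 2-12, add one model restricted to the induction visits: either an induction-only MMRM with the terms of SAP 7.3 or the ANCOVA at each visit, not both. If the MMRM is chosen, say which model gives the reported Week 12 estimate, since SAP 7.2 already has an ANCOVA there.
3. Report least squares mean differences from placebo with 95% CIs, and list the tables in both 9.4 and 9.4.1. Tables 14.2-2.5.1 and 14.2-2.5.3, and their 9.4.1 counterparts 14.2.2.5.1 and 14.2.2.5.3, could be extended to hold them.
4. Record in SAP 4.5, with a reason, any departure from Protocol 12.3.2 that remains.

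The cost is SAP wording and repeated use of code that already exists. The downside is up to 9 + 15 = 24 more unadjusted exploratory estimates at the 12-week cut. They will be imprecise, with a planned 9 subjects at each dose other than the recommended one and 15 on placebo, so they should be read as estimates with intervals and not as tests.

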7.3 Analysis of exploratory efficacy endpoints

All exploratory efficacy variables will be summarized by treatments. The changes from Baseline in mMES, UCEIS and total Mayo Clinic score as well as Baseline and Week 52 will be summarized by treatments. In addition, the partial Mayo Clinic scores (without sigmoidoscopy) and changes from Baseline will be summarized by study visit at Weeks 16, 20, 24, 28, 32, 36, 40, 44, 48, and 52 and at OLE/LTE Therapy Follow-up Period visits (Weeks 56, 60, and 64).

The change from Baseline in HRQL based on IBDQ will be analyzed for total score and 4 subscale scores at all study visits (Weeks 2 to 52, including Induction Therapy Follow-up Period visits (Weeks 16, 20, and 26) and OLE/LTE Therapy Follow-up Period visits (Weeks 56, 60, and 64).

Remission (mMES of 0 or 1, stool frequency subscore of 0 or 1 and rectal bleeding subscore of 0) rates at Week 12 will be summarized. Remission rates at Week 52 will be summarized by Double-Blind Period and OLE Therapy Period as well.

Clinical response and clinical remission will be summarized at Week 52. The percentage of subjects with mucosal healing, and the percentages of subjects with improvement in the mucosa (change from Baseline of at least a 1-point improvement in the mMES and/or in the modified Baron endoscopic scores) at Week 52 will be summarized by Double-Blind Period and OLE Therapy Period.

Durable clinical response and durable clinical remission at Week 52 will be summarized by Double-Blind Period and OLE Therapy Period. Durable clinical response and durable clinical remission at Week 52 will be defined as follows:

- Duration clinical response at Week 52 will be defined in the case that clinical response is present at both Weeks 12 and 52.
- Duration clinical remission at Week 52 will be defined in the case that clinical remission is present at both Weeks 12 and 52.

Glucocorticoid-free clinical remission at Week 52 will be summarized by Double-Blind Period and OLE Therapy Period. At Weeks 16 through 52 and through the OLE/LTE Therapy Follow-up Period (Week 56 through Week 64), the change from baseline in corticosteroid (glucocorticoid) dosages and the duration of glucocorticoid-free treatment will be summarized. Those parameters definitions are shown below.

- Glucocorticoid-free clinical remission at Week 52
 - Glucocorticoid-free clinical remission at Week 52 will be defined in the case that clinical remission is present at Week 52 and no glucocorticoid listed in Section 9.3 is used from Week 16 through Week 52.
- Glucocorticoid dosages:
 - Baseline glucocorticoid dosages (times) will be defined as the total number of administrations of glucocorticoid listed in Section 9.3 that is used during Double-Blind Induction Period (from Day 1 to a day before Week 16). For the subject who receives no glucocorticoid, the dosages will be 0.

	Forms			
	Title	Statistical Analysis Plan Template		
	Code	Version	Effective Date	Page
	FRM_ST03_032	01	23 Apr 2015	32 of 53

- Glucocorticoid dosages (times) at Week 16 through Week 52 will be defined as the total number of administrations of glucocorticoid listed in Section 9.3 that is used during OLE/LTE Therapy Period (from Week 16 to Week 52). For the subject who receive no glucocorticoid, the dosages will be 0.
- Glucocorticoid dosages (times) at Week 16 through LTE Therapy Follow-up Period will be defined as the total number of administrations of glucocorticoid listed in Section 9.3 that is used during LTE Therapy Period and LTE Therapy Follow-up Period (from Week 16 to Follow-up 3). For the subject who receives no glucocorticoid, the dosages will be 0.
- Glucocorticoid dosages (times) at Week 16 through OLE Therapy Follow-up Period will be defined as the total number of administrations of glucocorticoid listed in Section 9.3 that is used during OLE Therapy Period and OLE Therapy Follow-up Period (from Week 16 to Follow-up 3). For the subject who receives no glucocorticoid, the dosages will be 0.
- If there is glucocorticoid that the number of administrations is unknown, it will be assumed that the glucocorticoid was used at a frequency of an administration per day.
- For the subjects who do not move to OLE/LTE Therapy Period, “Glucocorticoid dosages (times) at Week 16 through Week 52” and “Glucocorticoid dosages (times) at Week 16 through OLE/LTE Therapy Follow-up Period” will not be defined.
- Change from baseline in corticosteroid (glucocorticoid) dosages will be defined as follows:
 - Change from baseline in corticosteroid (glucocorticoid) dosages at Week 16 through Week 52 = Glucocorticoid dosages at Week 16 through Week 52 - Baseline glucocorticoid dosages
 - Change from baseline in corticosteroid (glucocorticoid) dosages at Week 16 through LTE Therapy Follow-up Period = Glucocorticoid dosages at Week 16 through LTE Therapy Follow-up Period - Baseline glucocorticoid dosages
 - Change from baseline in corticosteroid (glucocorticoid) dosages at Week 16 through OLE Therapy Follow-up Period = Glucocorticoid dosages at Week 16 through OLE Therapy Follow-up Period - Baseline glucocorticoid dosages
- Duration of glucocorticoid-free treatment will be defined as the duration that no glucocorticoid listed in Section 9.3 is used from Week 16 through Follow-up 3.
 - Duration of glucocorticoid-free treatment (days) = Date of first glucocorticoid after Week 16 visit - Date of Week 16 visit
 - If the subject received glucocorticoid on the date of Week 16 visit, the duration of glucocorticoid-free treatment for the subject is 0.

A comparison between treatments (each KHK4083 dose level versus placebo) will be performed using an ANCOVA model with changes from Baseline in UCEIS, total Mayo Clinic score and partial Mayo Clinic score at Week 52 during Double-Blind Therapy Period as dependent variables, treatment as fixed effect and baseline value as covariate. The number of subjects and the number of subjects considered in the model will be provided by treatment. The adjusted means for treatments (least squares means) and the relative 95% CIs will be presented. The difference between the adjusted means for each treatment groups from placebo (Difference in Least Squares Mean from Placebo) will be calculated with the relative 95% CI and p-value. If ANCOVA cannot be applied

	Forms			
	Title	Statistical Analysis Plan Template		
	Code	Version	Effective Date	Page
	FRM_ST03_032	01	23 Apr 2015	33 of 53

due to the issue that the parameters cannot be estimated appropriately, these analyses using ANCOVA for Week 52 will not be applied.

Means with SDs for the efficacy variables (mMES, UCEIS, total Mayo score and partial Mayo score) at all visits will be performed graphically by each treatment (e.g. Placebo, 1.0 mg/kg, 3.0 mg/kg, or 10 mg/kg) and by Double-Blind Therapy Period and OLE Therapy Period. For partial Mayo score, Means with SDs as all visits will be performed graphically by “Double-Blind Therapy Period and Double-Blind Therapy Follow-up Period” and “OLE Therapy Period and OLE Therapy Follow-up Period”. Mean changes from Baseline will also be performed in the same manner.

To take into consideration about the repeat measurements in partial Mayo Clinic score, an analysis using a Mixed Model for Repeated Measures (MMRM) will be performed. A comparison between treatments (each KHK4083 dose level versus placebo) will be performed using a MMRM with the change from baseline in partial Mayo Clinic scores during Double-Blind Therapy Period and Double-Blind Therapy Follow-up Period as dependent variable, treatment as fixed effect and baseline value as covariate, and visit as random effects. The interaction between treatment and visit also will be included. An unstructured covariance matrix will be considered and the Kenward-Roger adjustment will be used for the degrees of freedom. In the case that the unstructured covariance matrix cannot be used, a compound symmetry will be used as the covariance matrix instead of the unstructured one. The number of subjects, the number of subjects considered in the model and the number of observations considered in the model will be provided by treatments. The adjusted means for treatments (least squares means) at each visit and the relative 95% CIs will be presented. The differences between the adjusted means for treatments from placebo (Difference in Least Squares Mean from Placebo) at each visit will be calculated with the relative 95% CIs and p-values. If MMRM cannot be applied due to the issue that the parameters cannot be estimated appropriately, the structure of covariance matrix will be changed to compound symmetry. If MMRM cannot be applied by using the covariance matrix of compound symmetry, this analysis using MMRM will not be applied.

SAS® code

```
proc mixed data=dat001 ORDER=DATA;
  class visit tmt;
  model chg=tmt visit baseline tmt*visit /solution ddfm=kr;
  repeated visit / type=un subject= subjectj;
  lsmeans tmt*visit / slice=tmt pdiff diff alpha=0.05 cl;
  lsmeans tmt / pdiff diff alpha=0.05 cl;
run;
```

For the following scores, to show changes in score during the study, those scores will be summarized by treatments.

- Subscores of Mayo Clinic Score other than mMES: “Stool Frequency”, “Rectal Bleeding”, and “Physician’s Global Assessment”
- Modified Baron Endoscopic Score
- Subscores of UCEIS: “Vascular pattern”, “Bleeding”, and “Erosions and ulcers”

	Forms			
	Title	Statistical Analysis Plan Template		
	Code	Version	Effective Date	Page
	FRM_ST03_032	01	23 Apr 2015	34 of 53

To show the differences between Investigational products in each cohorts, the efficacy variables (mMES, UCEIS, total Mayo score and partial Mayo score) at all visits will be summarized by treatments and cohorts.

